3. Subjects with Fitzpatrick Skin Type IV, V, or VI
4. Subjects with moderate to severe acne as defined by investigator-assessed Global Acne Assessment Score (GAAS) of 3 or 4 at screening
5. Facial acne vulgaris with 20 to 50 (inclusive) inflammatory lesions and 30 to 100 (inclusive) noninflammatory lesion
6. Stable non-progressive or regressive acne vulgaris in the investigator's opinion

7. Females of childbearing potential (FCBP) must have a negative pregnancy test at Screening and Baseline. A female is considered not to be of childbearing potential if she is post-menopausal with at least 12 consecutive months of amenorrhea or has undergone surgical sterilization. While on investigational product and for at least 28 days after taking the last dose of investigational product, FCBP who engage in activity in which conception is possible must use one of the approved contraceptive options described below:

Option 1: Any one of the following highly effective methods: hormonal contraception (oral, injection, implant, transdermal patch, vaginal ring); intrauterine device (IUD); tubal ligation; or partner's vasectomy;

OR

Option 2: Male or female condom (latex condom or nonlatex condom NOT made out of natural [animal] membrane [for example, polyurethane]); PLUS one additional barrier method: (a) diaphragm with spermicide; (b) cervical cap with spermicide; or (c) contraceptive sponge with spermicide.

8. Must be in general good as judged by the Investigator
9. Subject is willing to avoid excessive or prolonged exposure of the treated skin to ultraviolet light (i.e. sunlight, tanning beds) throughout the study
10. Subject is willing to follow study instructions and complete study assessments without assistance and is likely to complete all required visits

Exclusion:

1. Diagnosis of other dermatologic diagnosis that, in the opinion of the investigator, would interfere with diagnosis, examination, or treatment of the studied condition (i.e. psoriasis, atopic dermatitis, lupus, dermatomyositis, seborrheic dermatitis, perioral dermatitis, etc.)
2. Subjects with severe cystic acne, acne conglobate, acne fulminans, or secondary acne (chloracne or drug-induced acne)
3. Uncontrolled systemic disease(s) that, in the opinion of the investigator, would put the patient at significant risk if enrolled in the study or would interfere with subject's participation in the study

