4. Subjects with a history of clinically significant hemolysis, anemia, or enteritis (regional enteritis, ulcerative colitis, pseudomembranous colitis, antibiotic-associated colitis)
5. Subjects with allergy or sensitivity to the study drug or its components
6. Subjects who have not complied with the proper wash-out periods:
 - a. Topical anti-inflammatory medications, salicylic acid, corticosteroids, antibiotics, antibacterials, peroxide-containing products, or retinoids within 2 weeks of baseline
 - b. Systemic antibiotics, corticosteroids, antimalarials or oral dapsone within 4 weeks of baseline

- c. Other anti-acne medication, including isotretinoin or spironolactone, within 6 months of baseline
 - d. Chemical peels or other facial acne procedures (laser therapy, light therapy) within 3 months of baseline
 - e. Treatment with botulinum toxin of any serotype in the face within 6 months of baseline
 - f. Estrogens/Birth control pills must have been started ≥ 90 days prior to baseline and use must be continued during the study without alteration or discontinuation.
7. Pregnant or breastfeeding.
 8. Subjects with evidence of alcohol or substance abuse.
 9. Use of any investigational drug within 4 weeks prior to randomization, or 5 pharmacokinetic/pharmacodynamic half-lives, if known (whichever is longer).

c) Number of Subjects

Up to 40 subjects with acne vulgaris will be screened with a goal of 20 total subjects randomized. All 20 randomized subjects are expected to complete all study procedures. Individuals who provide informed consent and fail to meet all of the inclusion and exclusion criteria during the initial evaluation will be considered a “screening failure.”

d) Study Timelines

The study will consist of 6 in-person visits and one phone visit (7 total visits) over up to 28 weeks (4 week screening period plus 24 weeks enrolled in study). Study visits will be conducted at Screening (Visit 1), Baseline (Visit 2, Week 0), Week 4 (Visit 3), Week 8 phone visit (Visit 4), Week 12 (Visit 5), Week 18 (Visit 6), Week 24 (Visit 7).

Enrollment will occur over a 24-36 month period from January 2018 to December 2020. The study is anticipated to be completed by December 2021.

e) Endpoints

Primary Endpoint:

1. Mean change from baseline to week 12 in Global Acne Assessment Score (GAAS)

Secondary Endpoints:

1. Change from baseline in Global Acne Assessment Score (GAAS) at week 4, 18, and 24.

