2. Change from baseline in Post Acne Hyperpigmentation Index (PAHPI) at weeks 12, 18, and 24.
3. Change from baseline in Melanin Index (MI) of target lesion at weeks 12, 18, and 24
4. Change from baseline in the proportion of subjects with score of 0 or 1 on ASIS “dark spot” score at weeks 4, 12, 18, and 24.
5. Proportion of subjects with GAAS of 0 (none) or 1 (minimal) at weeks 4, 12, 18, and 24

6. Percent change from baseline in all lesion counts (inflammatory, noninflammatory, and total) at weeks 4, 12, 18, and 24.

f) Procedures Involved in the Human Research

This is a single-center, single-group, open-label study using Aczone® (dapson) gel 7.5%. All subjects will receive the study medication. Aczone® gel is an off-white to yellow gel with suspended particles. It is supplied in an airless pump containing a polypropylene bottle with a high density polyethylene piston. It will be dispensed as a 60g pump.

Subject will apply Aczone® once daily to the entire face. Study drug must not be applied to other areas of the body, including the upper chest, upper back or shoulders.

Prior to the start of the study, potential subjects will be given an IRB-approved Informed Consent Document (ICD) containing a Health Insurance Portability and Accountability Act (HIPAA) disclosure agreement to read, understand, and sign. All questions about the study should be answered to the satisfaction of the candidate subject. They will have all of their study-related questions answered by the PI or designee, and if they agree to participate, the subject will sign two original copies of the ICD. The subjects will retain one original copy and one original copy will be kept in the study file. The subjects who sign an ICD will be assigned a screening number.

After providing informed consent, subjects will be assessed for study eligibility at the Screening visit (day -28 to day -1), which includes review of medical history and concomitant, acne lesion counting and severity ratings, and serum pregnancy test (if applicable). The PI or a medically qualified designee must review this information (i.e. medical history, concomitant medication, and eligibility review) for each subject to confirm their eligibility before enrollment. A total of 20 subjects who meet eligibility criteria will undergo Baseline / Day 0 assessments. Subjects will return for visits at weeks 4, 12, 18, and 24. There will be a phone visit at week 8.

Study Assessments and Efficacy Measures:

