If a subject fails to report to the test facility for a scheduled visit and cannot be rescheduled within the permitted window of time (as applicable), the Site should consult with the Sponsor to determine if the subject should be documented as having withdrawn/dropped from the study.

Risks to Subjects

The following list of side effects is the ones that may be associated with the use of dapsone gel:

Common:

- Application site reactions:
 - Dryness
 - Peeling
 - Oiliness
 - Erythema
 - Pruritus
- Temporary yellow or orange discoloration of treated skin and local facial hair (when used in conjunction with benzoyl peroxide)

Rare:

- Methemoglobinemia – Cases of methemoglobinemia have been reported post-marketing in subjects using dapsone 5% gel twice daily. Initial signs and symptoms include slate grey cyanosis, which may be observed on the buccal mucous membranes, lips, and nail beds. Increased susceptibility to methemoglobinemia is seen patients with glucose-6-phosphate (G6PD) deficiency. The risk is also elevated in individuals taking other medications that induce the formation of methemoglobin (i.e. sulfonamides, acetaminophen, acetanilide, aniline dyes, benzocaine, chloroquine, naphthalene, nitrates and nitrites, nitrofurantoin, nitroglycerin, nitroprusside, pamaquine, para-aminosalicylic acid, phenacetin, phenobarbital, phenytoin, primaquine, quinine). Dapsone gel should be avoided in patients with known history of congenital or idiopathic methemoglobinemia. Patients should be instructed to discontinue use of dapsone gel immediately and seek medical attention if they develop any signs of cyanosis.
- Hemolysis – The use of oral dapsone has been associated with the development of hemolysis and hemolytic anemia, particularly in patients with G6PD deficiency. G6PD deficiency is most common in individuals of Mediterranean, African, South Asian, and Middle Eastern descent. Studies and post-marketing on dapsone gel has not demonstrated any clinically relevant hemolysis or hemolytic anemia in treated subjects. Lab changes suggestive of hemolysis have been seen in patients with G6PD deficiency using dapsone gel 5%. Dapsone gel should be used with caution in patients taking oral medications known to increase serum levels of dapsone, including trimethoprim/sulfamethoxazole, and should be avoided in patients taking oral dapsone and anti-malarial medications due to risk of hemolytic reactions.

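### The Risks section says to avoid dapsone gel with a history of congenital or idiopathic methemoglobinemia, but no eligibility criterion names that history

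*Combined protocol and SAP*

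**What the plan says.** Under the rare risks in Risks to Subjects, the protocol states: "Dapsone gel should be avoided in patients with known history of congenital or idiopathic methemoglobinemia".

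The criteria in section b) that come closest to this history are:

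- Inclusion 8: "Must be in general good as judged by the Investigator" (a word such as health appears to be missing).
- Exclusion 3: "Uncontrolled systemic disease(s) that, in the opinion of the investigator, would put the patient at significant risk if enrolled in the study" (a second limb covers disease that could disrupt taking part).
- Exclusion 4: "Subjects with a history of clinically significant hemolysis, anemia, or enteritis", the last term being followed by a list of bowel conditions.
- Exclusion 5: "Subjects with allergy or sensitivity to the study drug or its components".

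Three other places show how the list is used. Section c) says that people who consent but "fail to meet all of the inclusion and exclusion criteria during the initial evaluation will be considered a" screening failure. Section f) gives the check to the PI or to a delegate with medical qualifications, who "must review this information (i.e. medical history, concomitant medication, and eligibility review) for each subject to confirm their eligibility before enrollment". It then says: "A total of 20 subjects who meet eligibility criteria will undergo Baseline / Day 0 assessments".

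**The concern.** The Risks section identifies people in whom the study drug should be avoided. One would expect the list that governs entry to reflect that, and it does not. What is at stake is subject safety at the point of entry. Someone with this known history could meet every written criterion and receive the drug, although the same document says the drug should be avoided in that person. No endpoint, sample-size figure or analysis depends on the point.

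**Working it through.** There is no plan figure to reproduce. The check compares the Risks section with the eligibility list and then traces how the list controls entry.

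**Step 1: count the criteria.** Section b) has 10 inclusion and 9 exclusion criteria, and 10 + 9 = 19. Exclusion 6 has six wash-out sub-items (a to f), which were also read. Criteria naming methemoglobinemia: 0 of 19. The numbering is unbroken. The only text not available for this review lies between the data-management section and the safety-monitoring items, outside the list.

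**Step 2: test the nearest criteria.**

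| Criterion | What it covers | Requires exclusion for this history? |
|---|---|---|
| Inclusion 8 | General health, by investigator judgement | No; permits refusal |
| Exclusion 3 | Systemic disease that is uncontrolled, by investigator opinion | No; a known history need not be uncontrolled |
| Exclusion 4 | Hemolysis, anemia, enteritis | No; other conditions |
| Exclusion 5 | Allergy or sensitivity to the drug | No; other condition |

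Of these 4, 2 concern other conditions, 2 rest on judgement, and 0 name the history.

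**Step 3: compare with the section's other avoidance statement.** The hemolysis paragraph of the Risks section says the gel should also be avoided with oral dapsone and anti-malarial drugs. That statement has a counterpart in Exclusion 6b, a four-week wash-out for both. So one of the two populations or co-treatments that the section says to avoid is carried into the list and the other is not. No reason is given for the difference.

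**Step 4: trace entry.** A screening failure is defined by the criteria (section c). The medical-history review serves to confirm eligibility, and those who meet the criteria go on to Baseline (section f). Table 1 marks Inclusion/Exclusion at Visits 1 and 2, which is 2 of 7 visits, and Medical History at Visit 1 only. Drug Dispensation places the supervised first dose at Baseline, the second of those two visits. Nothing on this path requires anyone to act on the methemoglobinemia statement.

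**Step 5: look at what follows entry.** Later safeguards are adverse-event questioning at each visit and the Risks section's direction that patients stop and seek care if cyanosis appears. Both operate after exposure. Table 1 schedules no blood test directed at this risk.

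**The case against.** The best reply is that this is an omission and not a contradiction. The Risks section is itself protocol text, and Data Management and Confidentiality requires conduct according to the protocol. Resources Available says that all team members have read and understood it. An investigator who declines such a person therefore complies with everything written. The trigger is a known history, which is what the Screening medical history collects and what a medically qualified person must review. Inclusion 8 offers a ground for refusal, and Withdrawal of Subjects allows removal for safety at any time. Not every warning in a risks section has to become a numbered criterion. The study is also small, and by its own planned dates enrolment may be over.

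Much of this stands. It makes the route to dosing narrow, and a careful reviewer would probably refuse. It does not remove the mismatch. These safeguards permit refusal, or act after the first dose; none is a criterion that the person must fail. The drafting-preference argument is weakened by Exclusion 6b, which shows that the authors did carry the other avoidance statement into the list. The timing argument changes what the remedy is, but a remedy is still needed, and actual enrolment status is not stated.

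**Conclusion.** The concern holds. The Risks section says to avoid the drug in people with a specific known history, and 0 of 19 eligibility criteria name it. The textual absence is certain. The practical consequence is conditional: it needs a person with this history to present, to be judged in good health, and not to be refused on discretion. How often that would happen cannot be estimated, because the documents give no prevalence.

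This should be fixed as a matter of internal consistency with a bearing on subject safety. It has no effect on endpoints, power or analysis. The conclusion assumes that the eligibility list in the public document is the one applied at the site. A separate site checklist that already covers this history would remove the practical risk but not the inconsistency in the protocol.

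**What to change.** Reconcile the methemoglobinemia statement in Risks to Subjects with the criteria in section b) and the eligibility review in section f), so that the list applied at Screening and Baseline agrees with the Risks section. The sponsor's safety physician and the investigator should decide the clinical content; this review proposes none.

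If enrolment is open, the cost is a short protocol amendment, an updated eligibility checklist and IRB review. No new visit or test is needed, since medical history is already taken at Screening.

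Enrolment was planned to end in December 2020 and the study to be completed by December 2021, while the document is dated February 2022. If enrolment has closed, check the Screening medical-history records of the enrolled subjects (20 planned, from up to 40 screened) and document the result.

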Global Acne Assessment Score (GAAS):

The subject's acne severity will be assessed by the investigator using a 5-point GAAS at screening, baseline, and weeks 4, 12, 18, 24.

Grade	Description
0	None No evidence of facial acne vulgaris
1	Minimal Few noninflammatory lesions are present; a few inflammatory lesions (papules/pustules) may be present; no nodulo-cystic lesions present
2	Mild Several to many noninflammatory lesions are present; a few inflammatory lesions are present; no nodulo-cystic lesions present.
3	Moderate Many noninflammatory and inflammatory lesions are present; no nodulo-cystic lesions are present.
4	Severe Significant degree of inflammatory disease; papules and pustules are a predominant feature; a few nodulo-cystic lesions are present (no more than 2)

Lesion Counts:

The lesion counts, including inflammatory and non-inflammatory lesions, will be performed at screening, baseline, and weeks 4, 12, 18, and 24. Inflammatory lesions (papules, pustules, nodules/cysts) and

noninflammatory lesions (open comedone, closed comedone) will be counted individually. The sum of the inflammatory lesion counts and non-inflammatory lesion counts will be totaled.

ASIS ®:

Acne Symptom and Impact Scale (ASIS ®) will be given to subjects' for completion at baseline and weeks 4, 12, 18, and 24. The ASIS ® contains 9 items assessing symptom severity and 8 items assessing the psychosocial impact of acne vulgaris (6). High scores on the ASIS® indicate the presence of more severe symptoms, whereas higher scores on the ASIS indicate better outcomes on acne health-related quality of life.

PAPHI:

The postacne hyperpigmentation index (PAHPI) has been shown to be a reliable and valid score measuring post-inflammatory hyperpigmentation from acne (7). PAHPI will be scored using the following formula:

Total PAHPI = S + I + N

PAHPI Score can range from 6-22.

Lesion Size (S)

Weighted Score (S)	Median Lesion size
2	<3mm
4	3-6mm
6	7-10mm
8	>10mm

Lesion Intensity (I)

Weighted Score (I)	Median Lesion Intensity
3	Slightly darker than surrounding skin
6	Moderately darker than surrounding skin
9	Significantly darker than surrounding skin

Lesion Number (N)

Weighted Score (N)	Number of Lesions
1	1-15
2	16-30
3	31-45

4	46-60
---	-------

5	>60
---	-----

Melanin Index:

A narrowband reflectance spectrophotometer (mexameter MX-16) will be used to measure the degree of pigmentation of involved and adjacent uninvolved skin of one representative facial PIH lesion (8).

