6. N/A
7. N/A

8. Adverse events will be graded using the Common Terminology Criteria for Adverse Events (CTCAE).
9. The study will be conducted in compliance with regulatory requirements and Good Clinical Practice. Quality control will be applied to each stage of data handling to ensure that data are accurate, reliable and processed correctly.
10. Should a temporary or permanent suspension of our study occur, the occurrence will be reported to the PPHS, sponsor, and IRB.

Part II. Data Monitoring Committee/Data Safety Monitoring Board (DMC/DSMB)

Not applicable

j) Withdrawal of Subjects

When an individual who has signed the ICF is not enrolled in the study or withdraws/is withdrawn prior to completing the study, the reason is to be documented on the Discontinuation/Completion Form (or equivalent) and in the final study report. Reasons for subject withdrawal may include:

- Not enrolled (e.g. fails to meet inclusion/exclusion criteria, chooses not to enroll, etc.)
- Participant is determined to be ineligible after enrollment
- Subject's choice to withdraw
- Investigator terminated (e.g. noncompliance, etc.)
- Adverse Event
- Pregnancy
- Lost to follow-up
- Other

Subjects may withdraw from the trial at any time at their request, or they may be withdrawn at any time at the discretion of the Sponsor, PI, or designee for safety, behavioral, or administrative reasons. Subjects may be withdrawn from this study without their consent if the research study is being stopped; or if the instructions of the study team have not been followed.

If a subject does not return for a scheduled visit, *three documented attempts will be made to contact the subject in order to establish the reason for withdrawal, and* the outcome will be documented. The PI or designee should inquire about the reason for withdrawal, request that the subject return for a final visit, if applicable, and follow-up with the subject regarding any unresolved adverse events.

Should a subject withdraw from the trial and also withdraw consent for disclosure of future information, no further evaluations should be performed and no additional data should be collected. The PI and staff may retain and continue to use any data collected before such withdrawal of consent. Removed or withdrawn subjects will not be replaced.

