Study drug is stored in a combination-locked room accessible only by clinical trials personnel. All study materials should be stored at room temperature (59°-77°F), and the Site is responsible for maintaining temperature logs. All study products received and dispensed will be inventoried and accounted for throughout the study. The investigator must maintain adequate records documenting the receipt, use, loss, or other disposition of the products on the Product Accountability Log. The log must identify the investigational product and account for its disposition by subject, including specific dates and quantities dispensed and returned. The log must be signed by the individual who dispensed/retrieved the study product and copies must be provided to the sponsor for inclusion in the Trial Master File.

At the completion of the study, all units of product dispensed (whether empty or containing unused product) must be collected by the Site and returned, along with un-dispensed product, to the Sponsor. Any container not returned by the Site must be accounted for in writing.

k) Statistical Analysis Plan

The adverse events will be tabulated according to their date of onset, duration, severity and relationship to the treatment. We will build Clopper-Pearson 90% confidence intervals for the proportion of adverse events considering their aggregation and stratification (e.g., by severity).

Sample Size Considerations

A sample size of $n=20$ subjects allows $>90\%$ power at 5% significance level for a two-sided paired t-test to detect at week 12 a minimum change in GAAS from baseline of 1 grade point. This calculation was performed in G*Power and it assumes a mean GAAS of 3.5 at baseline and a maximal standard deviation of 0.513.

Analysis of primary Endpoint

The primary analysis will apply a two-sided paired t-test to assess the significance of the change in GAAS from baseline to week 12. However, GAAS is an ordinal measurement and, for this reason, we will also apply a Generalized Linear Mixed-effects Model (GLMM) to assess the significance of the changes in GAAS after including potential covariates.

Analysis of secondary Endpoints

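### Does the standard deviation of 0.513 in the sample-size statement undermine the claim of more than 90% power with 20 subjects?

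*Combined protocol and SAP*

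**What the plan says.** Section k) Statistical Analysis Plan, under Sample Size Considerations, opens with "A sample size of $n=20$ subjects allows" and claims a power above 90% at the two-sided 5% level "to detect at week 12 a minimum change in GAAS from baseline of 1 grade point". The calculation was done in G*Power, and "it assumes a mean GAAS of 3.5 at baseline and a maximal standard deviation of 0.513". No source is given for 0.513, and neither a week-12 SD nor a correlation between visits is stated.

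For the primary endpoint, the same section specifies the test as follows: "The primary analysis will apply a two-sided paired t-test to assess the significance of the change in GAAS from baseline to week 12".

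Three other places bear on the inputs:

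- Section b) requires an "investigator-assessed Global Acne Assessment Score (GAAS) of 3 or 4 at screening".
- Section f) has severity "assessed by the investigator using a 5-point GAAS at screening, baseline, and weeks 4, 12, 18, 24", with grades 0 to 4.
- Section c) says "All 20 randomized subjects are expected to complete all study procedures", and section j) says "Removed or withdrawn subjects will not be replaced".

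**The concern.** The paired t-test works on each subject's difference, so the variance that matters is that of the change from baseline to week 12. The plan offers one unlabelled SD next to the baseline mean and calls it maximal. Entry is limited to grades 3 and 4, and 0.513 is what 20 scores split evenly between those grades would give. If the figure describes baseline scores, it is a maximum for baseline only. After treatment the scores can spread over the whole 0 to 4 range, so the SD of change can be larger.

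This is the only justification given for 20 subjects. A reader who took 0.513 as a worst case for the change could think the power claim secure without knowing what it depends on. If the true SD of change were large enough, the trial would have less power than stated, and loss of subjects without replacement would reduce it further.

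**Working it through.** **Inputs.** From section k): n = 20, two-sided alpha 0.05, mean change 1 grade, SD 0.513. From sections b) and f): GAAS 3 or 4 at screening, 0 to 4 afterwards. The documents give no SD of change, so the values below other than 0.513 are assumptions that show a range.

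**Formula.** Power = P(T > t(0.975, n−1)), where T is noncentral t with n−1 degrees of freedom and noncentrality (1/SD of change) × √n. The opposite tail is negligible.

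**The plan's own figure.** With SD 0.513, the noncentrality is √20/0.513 = 8.72 and the critical value is 2.093. Power is above 99.99%, so the claim of more than 90% is reproduced. At that SD, six subjects would already give 96.4%.

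**Where 0.513 probably comes from.** Ten 3s and ten 4s have mean 3.5 and SD √(20 × 0.25/19) = 0.51299. A 9:11 split gives 0.510 and an 8:12 split 0.503, so the even split is the largest. The same calculation gives 0.5145 for n = 18 and 0.5118 for n = 22. The match is close, but it is an inference, because the document does not say so.

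**From score SD to change SD.** SD of change = √(s₀² + s₁₂² − 2·r·s₀·s₁₂), where s₀ and s₁₂ are the SDs at baseline and week 12 and r is their correlation. With 0.513 at both visits it is 0.513 at r = 0.5, 0.725 at r = 0, and at most 1.026 at r = −1.

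**A wider response.** Ten subjects unchanged and ten improving by 2 grades give a mean change of −1 and SD √(20 × 1/19) = 1.026. A broader spread (2 subjects worsening by 1 grade, 6 unchanged, 4 improving by 1, 6 by 2 and 2 by 3) gives mean −1, SD 1.21 and power of about 94%.

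| SD of change | Power, n = 20 |
|---|---|
| 0.513 | >99.99% |
| 0.725 | 99.99% |
| 1.0 | 98.9% |
| 1.026 | 98.5% |
| 1.2 | 94.2% |
| 1.3 | 90.3% |
| 1.5 | 80.7% |

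**Where the claim breaks.** Solving for 90% power at n = 20 gives an SD of change of 1.308, and 1.308/0.513 = 2.5. With a baseline SD of 0.513, the week-12 SD would have to exceed about 1.20 (r = 0), 1.37 (r = 0.3) or 1.49 (r = 0.5).

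**Loss of subjects.** The plan assumes none, so these counts are illustrative. The largest SD of change that keeps 90% power is 1.23 with 18 evaluable subjects, 1.15 with 16 and 1.07 with 14. At SD 1.026 the power is 95.3% with 16 subjects and 92.0% with 14.

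**Arithmetic ceiling.** With baseline scores split evenly between 3 and 4 and a mean change of −1, the largest possible sample SD of change is 2.41, where power is about 42%. That needs every grade-3 subject to worsen to 4 while three quarters of the grade-4 subjects clear to 0. It shows that 0.513 is not a mathematical bound, but it is not a plausible outcome.

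**The case for a change.** The strongest case for a change is that the plan gives the wrong kind of SD, or at least does not say which kind, in the one calculation that justifies the trial's size. The claim of more than 90% power is true only under a condition that appears nowhere: an SD of change no greater than about 1.31 with all 20 subjects, and less if some are lost. The stated inputs do not explain 20 either, since six subjects would have been enough. The phrase about a minimum change could also be misread, because the smallest mean change detectable with 90% power at those inputs is 0.39 grade. A sentence would put all this right.

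Part of this stands. The figure is unlabelled and unsourced, and it does not bound the SD of change. The rest is weaker:

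- If 0.513 is the baseline SD, as the arithmetic suggests, *maximal* is literally correct for 20 scores limited to 3 or 4. If it is an assumed SD of change, the documents contain nothing that contradicts it. It is false only if a baseline SD is being offered as a worst case for the change, and the text does not say that.
- One grade is the smallest step on the scale, so a minimum change of 1 grade reads naturally as the smallest change of interest.
- The completion assumption is stated openly, and any loss rate would be the reader's own choice.
- A stated ceiling of 1.3 would be back-solved from the power target and would not be evidence about the true SD.

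**Conclusion.** No change is needed. The sample-size sentence leaves out a label and a source, and a statistician reading it can fill the gap as above. The stated power is reproduced at the plan's inputs and survives an SD of change up to about 1.31 with 20 subjects. It also survives the largest value compatible with an SD of 0.513 at both visits (1.026), even with only 14 evaluable subjects. Better labelling would not alter the sample size, the test, the power claim or any conclusion.

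This rests on two assumptions. The first is that the SD of change lies below about 1.3, which the documents neither show nor contradict; above that value the claim would fail. The second is that baseline scores stay at 3 or 4. Eligibility fixes GAAS at screening, so a baseline score could differ. That affects the inference about where 0.513 came from, but not the power figures, which depend only on the SD of change.
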